- Official Title: Clinical, Radiographic and Histomorphotmetric Analysis of Healing Dynamics in Human Extraction Sockets Grafted With Bio-Oss Collagen®: A Prospective 3-year Post-loading Study
- NCT Number: NCT03659617
- Document Date: November 18, 2025

Objective: The purpose of this study is to clinically, radiographically and histologically evaluate the healing sequence of post-extraction sockets grafted with Bio-Oss Collagen® at 3, 6 and 9 months following tooth extraction in single-rooted tooth sites.

Design: This is a randomized clinical trial (NCT03659617). The study population consists of adult subjects (ages 18-95) that a single-rooted tooth (except the incisors of the lower jaw) indicated for extraction. Subjects cannot have significant heart, stomach, liver, kidney, blood, immune system disease, or other organ impairment or systemic diseases that would prevent undergoing the proposed treatment or may result in compromised healing (e.g. poorly controlled diabetes, active heavy tobacco use [>10 cigarettes/day])

Methods: Consented subjects will be randomized to one of three groups. Randomization will be done as 1:1:1. Therefore, subjects will have a 33% chance of being randomized to a group where they will have implant placement either after three, six, or nine months after implant placement.

Statistical Analysis Plan: The distribution of the data intergroup is expected to exhibit normality, and for this reason the statistical tests that will be utilized for data analysis are parametric. Nevertheless, prior to the conduction of any parametric test, Wilcoxon Signed Rank tests will be performed to verify the normal distribution of the data. Histomorphometric data will be expressed as the percentage of vital bone, remaining xenograft particles and non-mineralized connective tissue respective to the total sample area. The statistical analyses for these three different compartments will be performed independently: One-way Analysis of Variance (ANOVA) test will be performed to evaluate the differences in the percentage of each specific compartments between the three time points (3, 6 and 9 months). The percentage of each compartment evaluated will be the dependent variable and the time will be the independent variable. This test will probe the null hypothesis that is established as 'no difference in percentage of vital bone, remaining xenograft particles and non-mineralized connective tissue at the different harvesting time points'. The significance level will be set at 0.05 and the Bonferroni method for correction will be applied. False positive rate will be calculated, as well. The volumetric and linear data obtained from the CBCT scans will be analyzed using the same test utilized for the histomorphometric data analyses, setting the significance level at 0.05, the Bonferroni method will be applied and the false positive rate will be calculated. WHI values obtained at the three different time points (3, 6 and 9 months) will be analyzed using the Kruskal-Wallis test. The null hypothesis states that no differences in WHI will be found at different time points. Likewise, the self-

reported level of discomfort will be compared using the Kruskal-Wallis test. The level of discomfort and the post-op visits will be the dependent and independent variable respectively. The significance level will be set at 0.05. Other variables recorded in this study will be expressed as a percentage (i.e. implant survival rate) or presented using descriptive statistics (i.e. marginal bone level). These variables are not expected to be representative of meaningful changes and, consequently, no analytical statistics are initially planned. However, the data will be assessed upon collection and suitability of appropriate analyses will be determined upon data distribution.

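### The normality check named before every ANOVA, the Wilcoxon signed-rank test, does not test normality, and the plan states no fallback for those ANOVAs

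*Combined protocol and SAP*

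**What the plan says.** The Statistical Analysis Plan opens with an expectation: "The distribution of the data intergroup is expected to exhibit normality". It gives this as the reason for choosing parametric tests. It then adds a verification step: "prior to the conduction of any parametric test, Wilcoxon Signed Rank tests will be performed to verify the normal distribution of the data".

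The parametric tests that follow are one-way ANOVAs:

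- Histomorphometry: "One-way Analysis of Variance (ANOVA) test will be performed to evaluate the differences in the percentage of each specific compartments between the three time points". This is done separately for vital bone, residual xenograft and connective tissue, each as a percentage of the sample area.
- CBCT: "The volumetric and linear data obtained from the CBCT scans will be analyzed using the same test utilized for the histomorphometric data analyses".

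For both sets of outcomes the level is 0.05 with a Bonferroni correction. The Methods paragraph describes three parallel arms: "Randomization will be done as 1:1:1".

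No other normality check is named, and no other test is given for these outcomes if the check fails. Kruskal-Wallis is assigned only to WHI and self-reported discomfort. The closing remark about judging suitable analyses from the data distribution follows the variables planned for description only, such as implant survival and marginal bone level.

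**The concern.** The signed-rank test is a one-sample or paired test of location. Its null hypothesis is symmetry about a specified value, or about zero for paired differences. Normality is not part of that null. The three arms are independent, so the ANOVA comparison offers no natural pairing, and the plan gives no reference value.

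The plan rests its choice of parametric methods on normality and offers this test as the verification. If the test cannot verify normality, the safeguard is empty. Two analysts following the same sentence could also report opposite findings on the same data, depending on whether they centred the values first. Since no fallback is written down, whatever was done after a failed check would be decided once the data had been seen.

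**Working it through.** **Inputs.** From the document: the named test, the ANOVAs it precedes, the percentage scale, the 0.05 level and the 1:1:1 allocation. The document gives no sample size, SD or distribution, so there is no figure of the plan's own to reproduce. Arm sizes of 10, 15 and 30, the distributions below and a two-sided 0.05 level for the check are assumptions.

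**Step 1: what the statistic measures.** For a reference value m, rank the absolute differences |x − m| and sum the ranks of the positive ones. Under the null, each difference is equally likely to be positive or negative. Any distribution symmetric about m satisfies this, whether normal, flat or two-peaked.

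**Step 2: raw positive data against zero.** If every value is above zero, every sign is positive, and the exact two-sided p-value is p = 2 × (1/2)^n whatever the shape:

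- n = 6: 2/64 = 0.031
- n = 10: 2/1,024 = 0.0020
- n = 15: 2/32,768 = 0.00006

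Any all-positive sample of six or more is rejected. In simulation, normal data with mean 40 and SD 10 were rejected 100% of the time at n = 10, 15 and 30, as were the other shapes tried.

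**Step 3: data tested against their true centre.** With m = 40 and three shapes centred at 40, rejection stayed near the nominal level for all three, over n = 10 to 30:

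- normal: 3.5% to 5.0%
- uniform: 4.0% to 5.8%
- two-peaked: 4.4% to 5.5%

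The test cannot tell these shapes apart.

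**Step 4: data centred on the sample's own mean.** Percentage flagged as non-normal, with Shapiro-Wilk for comparison:

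| Data | n | Signed-rank | Shapiro-Wilk |
|---|---|---|---|
| Normal | 15 | 0% | 4% |
| Two-peaked | 15 | 0% | 100% |
| Lognormal, sigma 0.8 | 15 | 1% | 70% |
| Lognormal, sigma 1 | 15 | about 3% | about 82% |
| Lognormal, sigma 0.8 | 30 | 6% | 95% |
| Lognormal, sigma 1 | 30 | about 14% | about 99% |

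Centring on the median gives 0% for both two-peaked and lognormal data at n = 15, and about 30% for two-peaked data at n = 30.

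**Step 5: comparison.** The same normal sample fails in step 2 and passes in step 4. A strongly skewed sample of 15 also fails in step 2 and nearly always passes in step 4. The choice of reference value drives the answer.

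**The case against.** The best defence is that the misnamed check has no stated consequence. The plan commits to ANOVA for histomorphometry and CBCT and contains no rule that switches tests. That stands. A reader might infer that the choice between ANOVA and another test hangs on this check, but the document makes no such choice. What remains is that the only stated safeguard fails and nothing is specified to follow a failure.

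Second, no wrong inference has been shown. ANOVA tolerates moderate non-normality, and the simulations measure what the check misses, not ANOVA error. This also stands.

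Third, absolute statements about the test go too far. It does react to asymmetry in larger samples, as the n = 30 results show. Nor is it established that every outcome is positive: CBCT measures analysed as changes could be negative, and residual xenograft could be zero. Step 2 therefore applies to all-positive samples only. Likewise, the word intergroup does not establish that arms will be pooled for the check.

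Fourth, a reader might infer that the plan inflates type I error through unequal variances. That is a separate issue, which a valid normality test would not detect either, and it depends on assumed inputs. With assumed SDs of 1, 1.5 and 2, classical ANOVA error is about 8% to 8.5% for arms of 16/14/10, where the smallest arm has the largest SD. It is about 6% for equal arms, as 1:1:1 allocation intends, and about 4% for arms of 10/14/16. This range does not show an error in the plan.

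**Conclusion.** The sentence is wrong as written. The signed-rank test cannot verify normality, and its result depends on a reference value that the plan does not give. The size of the failure, as shown in the working, rests on assumed arm sizes and distributions. The conclusion does not, because it follows from the null hypothesis of the test.

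The consequence is limited. The stated support for the histomorphometric and CBCT ANOVAs is missing, and the analyst has no pre-specified alternative. The documents do not support the stronger reading that the ANOVA results would be invalid or that a planned analysis would be changed by the check. This should be fixed, but it does not by itself undermine the trial's main comparisons.

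**What to change.** Delete the signed-rank check and adopt one of two replacements.

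1. Keep a check. Assess residuals within arms by Q-Q plots and/or Shapiro-Wilk, and name in advance the analysis that replaces ANOVA if they are clearly non-normal, such as Kruskal-Wallis. State the criterion for switching.
2. Drop the pre-test. Pre-specify Welch one-way ANOVA for the histomorphometric and CBCT outcomes, with Kruskal-Wallis as a sensitivity analysis, and use residual plots for description only.

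The second option leaves less to judgement and also covers unequal variances, but the documents do not require it over the first. Its power cost is very small if variances are equal.

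Either option takes a sentence or two of SAP wording, with no new data and no change to trial conduct. It should be settled before outcome data are compared between arms. If analysis has already begun, the change and its date should be reported.

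### Bonferroni over the three arm pairs is valid but gives up power that a Welch global test followed by Welch pairwise tests at 0.05 would recover within 5% familywise error per outcome

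*Combined protocol and SAP*

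**What the plan says.** The Methods paragraph states: "Consented subjects will be randomized to one of three groups. Randomization will be done as 1:1:1". The arms differ in when the implant is placed: 3, 6 or 9 months. In the Statistical Analysis Plan section, a one-way ANOVA "test will be performed to evaluate the differences in the percentage of each specific compartments between the three time points". On the three tissue compartments the plan adds: "The statistical analyses for these three different compartments will be performed independently". The multiplicity rule is one sentence: "The significance level will be set at 0.05 and the Bonferroni method for correction will be applied". Linear and volumetric CBCT outcomes get the same test, "setting the significance level at 0.05, the Bonferroni method will be applied and the false positive rate will be calculated".

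The SAP does not say which comparisons Bonferroni covers, what the divisor is, whether pairs are tested only after a significant ANOVA, or whether tests are two-sided. On distribution it says "The distribution of the data intergroup is expected to exhibit normality", but it does not address equality of variances. It gives no sample size, SD, target difference or power, and mentions no closed or step-down procedure.

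**The concern.** The objective is to describe a healing sequence at 3, 6 and 9 months. A significant ANOVA says only that the arms are not all alike. Whether healing still progresses from 3 to 6 months, or from 6 to 9, has to be read from the pairwise comparisons, so their threshold matters.

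An ANOVA with a Bonferroni correction, applied to compartments analysed separately, is most naturally three arm pairs per outcome, each tested at 0.0167. With exactly three arms, 5% familywise error can be kept with a less strict pairwise threshold, using the global test that is already planned. What is at stake is power to say which interval changed. The validity of the plan is not in question.

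**Working it through.** **Inputs.** From the documents: three arms, 1:1:1, one-way ANOVA per outcome, alpha 0.05, Bonferroni. Assumed, because the documents are silent: 10 to 30 per arm, normal data, differences in SD units, two-sided tests. The plan states no power or sample-size figure, so there is nothing to reproduce.

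**Bonferroni threshold** on the three-pair reading: 0.05/3 = 0.0167 per pair.

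**Why 0.05 per pair suffices after a significant global test.** Call the pairwise nulls H(3,6), H(6,9) and H(3,9). If any two are true, all three means are equal, so every intersection of two is the global null. The closed family is therefore the global null plus the three pairs. Three cases cover everything:

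- All means equal: a false claim first needs the global test to reject, probability at most 0.05.
- Exactly one pair equal: a false claim needs that pair's own test to reject, probability at most 0.05.
- No pair equal: no false claim of a difference is possible.

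This is special to three arms. With four arms, three of them equal, a significant F followed by pairs at 0.05 gave about 12% error in simulation. With three arms and no global test first, three pairs at 0.05 gave about 12% when all means were equal.

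**Simulated familywise error** (pooled-variance tests, equal SDs, 200,000 trials per scenario):

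| Truth | Closed (F at 0.05, then pairs at 0.05) | Bonferroni at 0.0167 |
|---|---|---|
| All means equal | 4.9–5.0% | about 4.3% |
| One arm differs | 4.7–5.0% | about 1.7% |

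**Simulated power, one arm differing from the other two by 1 SD** (per true pair, pooled-variance tests; Holm from 100,000 trials):

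| n per arm | Bonferroni | Holm | Closed | Closed minus Bonferroni |
|---|---|---|---|---|
| 10 | 39% | 42% | 49.5% | about 10 points |
| 15 | 60% | 63% | 71% | 11 points |
| 20 | 75% | 79% | 84.5% | about 9 points |
| 30 | 92% | – | 96% | 4 points |

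**Steady rise of 0.5 SD per interval, n = 15:** adjacent pairs 14% with Bonferroni, 25% closed; extreme pair (3 v 9 months) 60% and 64%.

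**Unequal variances.** False rejection of the one true pairwise null with the third arm far away, pooled-variance tests, n = 10 to 20, assumed SDs:

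| SDs | Closed, pooled | Bonferroni, pooled |
|---|---|---|
| 1.5, 1.5, 1 | 7.6% | 3.0% |
| 2, 2, 1 | 8.8% | 3.8% |
| 2, 2, 0.5 | 10.4% | 4.8% |

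With Welch ANOVA and Welch t-tests the closed procedure returned to 4.9–5.0% at SDs 2, 2, 0.5. With equal SDs and n = 15, Welch-closed power was about 69% (68.5%) against about 58% (57.5%) for Welch with Bonferroni, a gain of 11 points. Against pooled Bonferroni at 60%, the net gain is 68.5 − 60 = 8.5 points.

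**As sample size.** For one pair, 80% power and a 1 SD difference, normal approximation n = 2(z₁₋α/₂ + 0.84)²: at 0.0167, 2(2.394 + 0.842)² = 20.9, so 21 per arm; at 0.05, 2(1.960 + 0.842)² = 15.7, so 16. The 16 is a lower bound, because the global test must also reject.

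**The other reading of the family.** If Bonferroni was meant across the three compartments, one 0.05 test per compartment without it gives 1 − 0.95³ = 14.3% if they were independent, and about 10–13% in simulations where the compartments sum to 100%. The closed procedure over arms does nothing about that.

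**The case against.** The strongest objection is that the three-pair reading is inferred. The SAP names no pair and no divisor, and its Bonferroni sentence follows a null hypothesis covering all three compartments. A correction across compartments is therefore possible, and removing it would leave that family uncontrolled. This stands. Separate analysis of the compartments favours the three-pair reading, but the SAP has to settle the matter.

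Second, Bonferroni's slack has a use: with pooled tests and unequal SDs it stays below 5% in the far-arm settings above, where the closed procedure does not. This also stands, and it is why Welch tests must be part of the change and not an option. With Welch tests the objection is met.

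Third, Bonferroni comes with matching simultaneous confidence intervals, which a descriptive healing study may value. That is a real cost.

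Fourth, the gain rests on assumed figures, is only 4 points for the extreme pair in the steady-rise case, and leaves adjacent-pair power at 25%. True; the figures are illustrations.

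A reader might also infer that the plan spends alpha twice, once on the ANOVA and again on the pairs. The documents do not support this. They do not say that pairs wait for a significant ANOVA; and if they do, requiring it changes Bonferroni power by at most 0.4 points. The loss comes from the 0.0167 threshold. Nor is the closed procedure better in every single trial: if Bonferroni is applied without requiring the ANOVA, it rejects some pair when F does not in about 0.4% of simulated trials or fewer.

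**Conclusion.** The point holds as a suggestion for a better method. On the natural reading, the plan's Bonferroni correction is valid but stricter than 5% familywise error per outcome requires. At an assumed 10 to 20 per arm with one arm differing by 1 SD, the like-for-like gain is about 9 to 11 points per true pair, or 3 to 4 with Holm. The size in this trial is unknown, because the plan gives no sample size, SD or effect size.

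Two stronger readings should be resisted. The SAP does not state that each pair is tested at 0.0167; that is an inference. And the plan does not contain an error here: its error control under equal variances is sound, and the issue is efficiency. The 5% control claimed for the alternative applies to each outcome separately, not across compartments or across histology and CBCT, and with Welch tests it is approximate.

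**What to change.** For each histomorphometric and CBCT outcome, state in the SAP that the family is the three arm pairs; that the global test is Welch ANOVA at 0.05; and that only if it is significant are 3 v 6, 6 v 9 and 3 v 9 months each tested at two-sided 0.05 by separate-variance (Welch) t-tests. The condition on the global test must be written out, because the 0.05 pairwise level is not justified without it.

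If the sponsor prefers adjusted p-values, use Holm in place of Bonferroni for the three pairs, again with Welch tests, since Holm can also end by testing the last pair at 0.05. If the correction was meant across the three compartments, say so and use Holm for that family; it is never less powerful than Bonferroni.

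The cost is a few sentences of SAP wording and the loss of matching simultaneous intervals, so unadjusted 95% confidence intervals must be labelled as unadjusted. If SDs are in fact equal, Welch tests cost about 2 points of power at n = 15 (71% to 69%). The wording should be fixed before outcome data are examined by arm.

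### The CBCT outcome is left undefined and goes to one-way ANOVA with no baseline or site covariate, which may cost precision

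*Combined protocol and SAP*

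**What the plan says.** The Statistical Analysis Plan section first sets the test for histomorphometry: "One-way Analysis of Variance (ANOVA) test will be performed to evaluate the differences in the percentage of each specific compartments between the three time points". Its model terms follow: "The percentage of each compartment evaluated will be the dependent variable and the time will be the independent variable". The CBCT outcomes are then given the same treatment: "The volumetric and linear data obtained from the CBCT scans will be analyzed using the same test utilized for the histomorphometric data analyses", with the error rate handled by "setting the significance level at 0.05, the Bonferroni method will be applied and the false positive rate will be calculated".

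No covariate, stratification factor or baseline scan is mentioned for the CBCT data. The section does not say whether the analysed quantity is a dimension at follow-up, an absolute change or a percentage change.

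The Design paragraph admits adults with "a single-rooted tooth (except the incisors of the lower jaw) indicated for extraction". The Methods paragraph says "Randomization will be done as 1:1:1", the three groups being the 3-, 6- and 9-month times, and mentions no stratification by tooth or jaw.

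**The concern.** One-way ANOVA on group is a natural choice for histomorphometry. Each compartment is a percentage of the sample area and has no earlier value of its own.

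CBCT widths, heights and volumes are different. A site has a size before any healing starts, and the entry rule lets that size vary from upper incisors to canines and single-rooted premolars in either jaw. If raw follow-up dimensions are compared, original site size goes into the error term. Any chance difference in site mix between the three groups stays in the estimated differences.

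Leaving the outcome undefined adds to this. Raw value and change can have quite different precision, and the choice stays open until the data have been seen.

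**Working it through.** **No planned figure to reproduce.** The documents state no sample size, power, effect size, SD or correlation. What follows shows what adjustment would be worth under stated assumptions.

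**Inputs from the documents:** three groups, 1:1:1 allocation, significance level 0.05, group as the only factor.

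**Assumptions:**
- A CBCT scan at or before extraction or grafting exists for each patient.
- Baseline and follow-up have the same within-arm SD, σ.
- Their within-arm correlation ρ lies between 0.3 and 0.8.

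**Step 1. Residual variance under each choice**
- Raw follow-up value: σ²
- Change score: 2(1 − ρ)σ²
- ANCOVA on baseline: (1 − ρ²)σ²
- ANCOVA relative to change: (1 − ρ²) / [2(1 − ρ)] = (1 + ρ)/2

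| ρ | Change / raw | ANCOVA / raw | ANCOVA / change |
|---|---|---|---|
| 0.3 | 1.40 | 0.91 | 0.65 |
| 0.5 | 1.00 | 0.75 | 0.75 |
| 0.7 | 0.60 | 0.51 | 0.85 |
| 0.8 | 0.40 | 0.36 | 0.90 |

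ANCOVA therefore removes 9% (ρ = 0.3) to 64% (ρ = 0.8) of the variance of raw values, and 35% to 10% of the variance of change scores over the same range. The two gains run in opposite directions as ρ rises.

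**Step 2. The same gain as a sample-size factor**
- Against raw values, 1/(1 − ρ²): 1.10 at 0.3, 1.33 at 0.5, 2.78 at 0.8.
- Against change scores, 2/(1 + ρ): 1.54 at 0.3, 1.33 at 0.5, 1.11 at 0.8.

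**Step 3. What leaving the outcome undefined can cost.** The second column of the table compares the two readings of the current text. At ρ = 0.3, analysing change instead of the raw value raises variance by 40%. At ρ = 0.8 it lowers variance by 60%. The plan gives no basis for knowing which applies.

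**Step 4. Power illustration.** Assume 15 patients per group (N = 45) and Cohen's f = 0.40 on the raw scale. Neither figure is in the documents. Use the noncentral F with 2 numerator degrees of freedom at level 0.05. Error degrees of freedom are 45 − 3 = 42, or 41 with the baseline covariate. The noncentrality for raw values is 45 × 0.40² = 7.2; for the other two analyses, divide 7.2 by the variance ratio from Step 1.

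| Analysis | ρ = 0.3 | ρ = 0.5 | ρ = 0.7 |
|---|---|---|---|
| Raw follow-up | 63.5% | 63.5% | 63.5% |
| Change score | 48.6% | 63.5% | 85.8% |
| ANCOVA | 67.8% | 76.7% | 91.0% |

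These are omnibus powers for one outcome, before any Bonferroni correction. They ignore the small variance that chance baseline imbalance adds to adjusted differences.

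**The case against.** The best defence is that nothing here is an error. Groups are randomised, so one-way ANOVA is a valid test and its group differences are unbiased in expectation. Chance imbalance in site size is already allowed for in its error term. The gain from adjustment is of unknown size, and at ρ = 0.3 it is only 9% of variance against raw values. The CBCT variable may also turn out to be a change from baseline, in which case each site's starting size is already used. All of that stands. It makes this a point about efficiency and definition, not validity.

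It does not remove the point. Under either reading of the outcome, ANCOVA is at least as efficient, apart from the degrees of freedom spent.

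Several stronger readings are tempting but unsupported:
- *Site variation swamps the healing effect.* This needs a between-site SD and an effect size, and neither is given.
- *Adjustment is worth 2.8 times the sample size.* That holds only if raw values are planned and ρ is 0.8. Against change scores at the same ρ, the factor is 1.11.
- *The trial is small, or baseline size is the strongest predictor of later size.* The documents state neither.
- *Repeated scans from one patient are treated as independent.* The 3-, 6- and 9-month times are randomised groups, and nothing says that several CBCT scans per patient enter this test.
- *The baseline data are already recorded.* No baseline scan is mentioned, so this can only be assumed.

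**Conclusion.** The point holds as one of precision and outcome definition. The CBCT outcome is undefined, the planned model has group as its only term, and no baseline or site covariate is named despite a mixed set of eligible tooth sites. The planned test remains valid under randomisation.

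The loss may be anything from minor to large: 9% to 64% of residual variance if raw values are meant, and 35% to 10% if change scores are meant, as ρ goes from 0.3 to 0.8. Those ranges depend on the assumed correlation, on equal variances at the two scans, and on a baseline scan existing. They do not cover percentage change, which the text also leaves possible. The correction is specific and cheap, so it should be made, but the trial's conclusions do not stand or fall on it.

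**What to change.** Amend the CBCT sentence in the Statistical Analysis Plan, before CBCT data are compared by arm, to state:

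1. The scan times, and the outcome as one follow-up value per patient for each volumetric or linear measure, taken at the patient's assigned time (3, 6 or 9 months).
2. If a scan at or before extraction or grafting exists: ANCOVA with randomised arm, the same site's baseline CBCT value and one prespecified site covariate. Tooth type matches the source of variation more closely. Jaw is cheaper but does not separate incisors, canines and premolars.
3. If no baseline scan exists: say so, and adjust for tooth site only.
4. Adjusted differences between arms with 95% CIs, alongside the planned test.

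**Cost.** The baseline value takes one degree of freedom, jaw one more, and a three-level tooth type two. In the illustration with 45 patients, error degrees of freedom fall from 42 to 40 (baseline and jaw) or 39 (baseline and tooth type). Otherwise the cost is SAP wording and a small amount of extra analysis, provided that the baseline scan and tooth position are on record. The documents do not confirm this.

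### Self-reported discomfort is to be compared across post-operative visits with Kruskal-Wallis, a test for independent groups, although the wording implies that the same patients are scored at each visit

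*Combined protocol and SAP*

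**What the plan says.** The Statistical Analysis Plan section of the combined protocol and SAP treats two outcomes with Kruskal-Wallis, one after the other.

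- Wound healing index: "WHI values obtained at the three different time points (3, 6 and 9 months) will be analyzed using the Kruskal-Wallis test".
- Discomfort, introduced as being handled likewise: the self-"reported level of discomfort will be compared using the Kruskal-Wallis test". The next sentence defines the variables: "The level of discomfort and the post-op visits will be the dependent and independent variable respectively". Then: "The significance level will be set at 0.05".

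The Methods paragraph gives the design: "Consented subjects will be randomized to one of three groups", and "Randomization will be done as 1:1:1". The groups differ in when the implant is placed (three, six or nine months).

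The section names no patient effect, blocking or repeated-measures method. The documents contain no list of post-operative visits, discomfort scale or sample size. The closing remark that further analyses may be chosen once data are in hand concerns the other variables, such as implant survival and marginal bone level, and does not cover discomfort.

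**The concern.** Kruskal-Wallis compares independent samples. With visit as the factor, its groups would be the scores at one visit, the next visit, and so on. If one set of patients supplies them all, the scores are paired. Patients who tend to report more discomfort do so at every visit. That between-patient spread cancels out of the differences between visits, but Kruskal-Wallis keeps it in the variance by which it judges them. The statistic is then too small and the p-value too large.

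At stake is the reading of a null result. A genuine fall in discomfort after surgery could be reported as no difference because the test was poorly matched to the data.

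**Working it through.** **Inputs from the documents.** Test: Kruskal-Wallis. Factor: post-operative visit. Level: 0.05. There is no power or sample-size figure to reproduce, so the check is whether the planned test keeps its stated 5% level.

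**Assumptions, not in the documents.** 30 patients, K = 4 visits, normally distributed scores with equal correlation ρ between any two visits of one patient, and a linear fall from first to last visit.

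**Step 1: approximate level.** With equal correlation, differences between visit means have variance proportional to 1 − ρ, while the test scales them by the full variance. Under no visit effect the statistic therefore behaves roughly as (1 − ρ) times a chi-square on K − 1 degrees of freedom, and

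actual level ≈ P(χ² with K − 1 df > critical value / (1 − ρ)).

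For K = 4 the 5% critical value on 3 df is 7.815.

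- ρ = 0.3: 7.815 / 0.7 = 11.16, level 0.011
- ρ = 0.5: 7.815 / 0.5 = 15.63, level 0.0014
- ρ = 0.7: 7.815 / 0.3 = 26.05, level about 0.00001

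The formula treats ranks as if they were the scores themselves, so simulation is needed for the actual size.

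**Step 2: simulated level and power (30 patients, 4 visits).** KW is Kruskal-Wallis by visit; Friedman ranks within patient.

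| ρ | KW actual level | Power, 0.5 SD fall, KW v Friedman | Power, 1.0 SD fall, KW v Friedman |
|---|---|---|---|
| 0.3 | 1.3% | 27% v 39% | 94% v 95% |
| 0.5 | 0.3% | 20% v 53% | 95% v 99% |
| 0.7 | under 0.1% | 14% v 76% | 98% v 100% |

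The share of available power lost for the 0.5 SD fall is (39 − 27)/39 = 31%, (53 − 20)/53 = 62% and (76 − 14)/76 = 82%.

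**Step 3: sensitivity.** The following use scores rounded to a 0–10 scale, with 30, 45 or 60 patients and 3 or 4 visits.

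- Friedman's actual level stayed between 4.4% and 5.1% in every setting.
- At ρ = 0, Kruskal-Wallis ran at 4.3% to 5.4%, so the fault comes from the correlation and not from the rank test itself.
- For a 0.5 SD fall at ρ = 0.5, power was 46% against 73% with 45 patients and 3 visits, and 57% against 86% with 60 patients and 4 visits.
- At ρ = 0 with 30 patients and 4 visits, Kruskal-Wallis was slightly ahead, 33% against 29%.

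With normal scores at ρ = 0.1, 60 patients, 4 visits and a 0.5 SD fall, Kruskal-Wallis was again slightly ahead, 65% against 59%.

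**The case against.** **The factor may have been meant as the randomised group.** The discomfort sentence follows the wound healing sentence and is tied to it by its opening word; that sentence uses 3, 6 and 9 months, the same labels as the arms. On that reading the samples are independent and Kruskal-Wallis is suitable. This cannot be excluded. But the next sentence names post-operative visits as the independent variable, and an analyst would follow it. If groups were meant, the plan names the wrong variable and still needs correcting.

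**Repeated scoring is inferred, not stated.** This stands. No visit schedule is given. The plural, with visit as the factor, makes repeated scoring the natural reading, but the point is conditional on it.

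**The error is conservative.** This also stands. A reader might infer that a test which ignores correlation produces false positives. Here it does the opposite, so a significant result would not be undermined; only a non-significant one is hard to interpret.

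**A reader might infer that the test loses most of its power.** That holds only for a modest effect with moderate to high correlation. It fails for a 1.0 SD fall and for weak correlation, and none of these quantities is in the documents.

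**A reader might also infer that leaving out the randomised arm is an error.** A by-visit test does not compare the arms. However, the Objective concerns clinical, radiographic and histological healing, and nothing in the document promises a between-arm comparison of discomfort. Describing discomfort over visits is a legitimate question in itself.

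**Conclusion.** The point holds on the plan's literal wording, conditional on the same patients being scored at several visits. The p-value from the planned test would then be wrong in the conservative direction. With 30 patients and 4 visits, the actual level would be about 1.3% to under 0.1% for correlations of 0.3 to 0.7. The power cost for a 0.5 SD fall runs from about a third to about four fifths of what Friedman offers, and shrinks to a few percentage points at most for a 1.0 SD fall. All these sizes depend on the assumed sample size, visits, correlation and effect.

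This is a should-fix matter. Discomfort is not presented as a main outcome, the false-positive rate is not raised, and the histomorphometric and CBCT comparisons are untouched. The two readings of the factor lead to different tests, so the text needs correcting whichever was intended.

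**What to change.** 1. List the post-operative visits at which discomfort is recorded, say after which procedure each falls, and state the scale.
2. If change over visits is the question, replace Kruskal-Wallis with a Friedman test with patient as the block. It needs complete data for each patient. If missed visits are expected, use an ordinal mixed model with a patient effect and a visit term, which keeps patients with partial data.
3. If the randomised 3-, 6- and 9-month groups were meant, correct the independent variable to the group, define one discomfort score per patient, and keep Kruskal-Wallis.
4. Optionally, add a between-arm comparison on a per-patient summary such as the mean or peak score, or state that discomfort is not compared between arms. A model with visit-by-arm terms is not needed for the stated question and could be unstable in a small trial.

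The cost is a few sentences of SAP text and slightly more programming. No new data are needed.
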